7.3.4 FINAL STUDY VISIT

Follow up phone call at week 7:

Record for adverse events as reported by the participants.

Record current medication

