Secondary Obective:

To evaluate effect of fluoxetine on HCVR and peri-ictal respiratory

depression in drug resistant epilepsy patients.

Version 01.2 Protocol:201607761 Version 01.2

Endpoint Primary End point:

Study recruitment rate assessed every 3 months through the study

completion

Study retention rate assessed every 3 months through the study completion

Secondary End point:

Change in mood score using PHQ-9 score

Change in minute ventilation during HCVR testing

Change in slope of HCVR

Difference in duration of abnormal breathing in periocal period

Difference in oxygen saturation during periotal period

Difference in CO₂ level in periotal period

Exploratory End points: Change in VRTCO₂

Change in time to VRTCO₂

Change in time to end of HCVR testing

Population: Subjects age 18-75 years, both genders, drug resistant epilepsy with no

prior severe depression or other psychiatry co-morbidities but otherwise healthy, mostly living in State of Iowa will be screened for this study.

Phase: 2 Number of Sites 1

enrolling participants:

[figure not shown]
Description of Study Fluoxetine, given by mouth with a standard titration over 6 weeks.

Agent: 10 mg for 1 week, 20 mg for 1 week, 40 mg for 2 weeks, 20 mg for 1 week,

10 mg for 1 week then STOP

Study Duration: 2 years **Participant Duration:** 6 weeks

Version 01.2 Protocol:201607761 06/28/2017

Version 01.2 Protocol:201607761 06/28/2017

I KEY ROLES

[name]

Role: Principal investigator

Institution: The University of Iowa,

Address: [name]

[contact] Email: [contact]

[name] Role: Co-Investigator

Institution: The University of Iowa,

Address: [name]

[contact] Email: [contact]

[name] Role: Co-Investigator

Institution: The University of Iowa,

Address: [name]

[contact] Email: [contact]

[name] PhD

Role: Co-Investigator

Institution: The University of Iowa,

Address: [name]

[contact]

Email: [contact]

[name] [name] Role: Biostatistician

Institution: The University of Iowa,

Address: [name]

[contact] Email: [contact]

[name] PhD

Role: Independent Medical Examiner Institution: The University of Iowa,

Address: [name]

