6.1.7 STARTING DOSE AND DOSE ESCALATION SCHEDULE

10 mg once a day for one week, 20 mg once a day for one week, 40 mg once a day for two weeks, 20 mg once a day for one week and 10 mg once a day for one week. Then STOP.

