6.1.8 DOSE ADJUSTMENTS/MODIFICATIONS/DELAYS

Subjects will be allowed to take 40 mg/day of drug vs placebo for maximum of an extra 1 week in case of delay in follow up appointment.

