6.1.9 DURATION OF THERAPY

6 weeks

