7.3.2 ENROLLMENT/BASELINE

- Obtain informed consent of potential participant verified by signature on study informed consent form
- Verify inclusion/exclusion criteria.
- Obtain urine pregnancy test when applicable.
- Obtain demographic information, medical history, medication history, alcohol and tobacco use history.

Version 01.2 Protocol:201607761 Version 201.2

- Perform HCVR testing
- PHQ-9 score
- Randomize to one of the intervention arm
- Discharge randomized subjects with assigned treatment with one week of 10 mg, one week of 20 mg and 4 weeks of 40 mg pills.

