7.3.3 FOLLOW-UP

Follow up phone call at end of week 1 and 3

Record for adverse events as reported by the participants.

If suspicious for mania, will perform full Altman self-report maniac scale

Record compliance to assigned treatment as reported by the participants.

Record current medication

Follow up visit 4 weeks (+/-1 week) after randomization

Record for adverse events as reported by the participants.

Record compliance to assigned treatment as reported by the participants and by counting pill from the pill container brought by the participants.

Record PHQ-9 score

Repeat HCVR testing

Record current medication

Video EEG study with comprehensive respiratory monitoring in EMU for paticipants enrolled at neurology clinic

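### The last adverse-event call stays at week 7 even when the permitted extra days at 40 mg push back the last dose

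*Combined protocol and SAP*

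**What the plan says.** - **Dose schedule (6.1.7, repeated in the Protocol Summary).** One week at 10 mg, one at 20 mg, two at 40 mg, then a taper: "20 mg once a day for one week and 10 mg once a day for one week. Then STOP". The Summary describes the drug as "given by mouth with a standard titration over 6 weeks", and Section 6.1.9 also gives six weeks of therapy.
- **Extension (6.1.8).** The 40 mg dose may continue "for maximum of an extra 1 week in case of delay in follow up appointment". The section does not say whether the full taper follows.
- **Contacts (7.3.3, 7.3.4).** Calls: "Follow up phone call at end of week 1 and 3". Visit: "Follow up visit 4 weeks (+/-1 week) after randomization". Final contact: "Follow up phone call at week 7", recording AEs and current medication. The schedule table (7.3.7) shows no later AE contact, and the early termination visit (7.3.5) is not applicable.
- **AE recording (8.3).** Events are recorded for a further week beyond the end of participation. Active questioning is tied to the scheduled visits and calls.
- **Supply (7.3.2).** Participants leave with "one week of 10 mg, one week of 20 mg and 4 weeks of 40 mg pills". This conflicts with 6.1.7, since it lists no taper pills, although both add up to 42 days.

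**The concern.** The final call is fixed at a nominal week, while the last dose can move by up to seven days under the protocol's own provision. Nothing connects the two. On any reading that keeps the full taper, participants with the longest exposure at 40 mg (up to 21 days instead of 14) get the shortest active inquiry after their last dose.

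The protocol treats stopping the drug as a risk. Section 2.3.1 lists symptoms of abrupt discontinuation, and Section 7.4 gives withdrawal symptoms as one reason for the dose schedule. At stake is the active collection of events after the last dose in extended participants. The arm comparison and the recruitment and retention endpoints are not affected.

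**Working it through.** **Inputs.** Dose steps from 6.1.7; extra days at 40 mg, d = 0 to 7, from 6.1.8; the upper visit limit of one week late from 7.3.3, which matches d = 7; the final call at week 7 from 7.3.4. Day 1 is the first dose, assumed to be at randomization.

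**Reproducing the plan's duration.** 7 + 7 + 14 + 7 + 7 = 42 days, which agrees with the six weeks in 6.1.9. The supply in 7.3.2 gives 7 + 7 + 28 = 42 days, so the on-time last dose is the same under either text. The supply text does not settle the last dose of an extended participant; I follow 6.1.7.

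**Last dose with a full taper.** 7 + 7 + (14 + d) + 7 + 7 = 42 + d.

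**Which day is week 7?** The text does not say. Day 49 is plausible: the Protocol Summary gives a six-week participant duration, and 42 days plus the 7 in Section 8.3 is 49. But the earlier calls are placed at the end of a week and this one is not, so day 43 is also possible.

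**Three readings.** Drug-free days = call day − last dose day.

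- A: call on day 49, full taper kept: 49 − (42 + d) = 7 − d.
- B: call on day 43, full taper kept: 43 − (42 + d) = 1 − d.
- C: therapy capped at 42 days: 49 − 42 = 7, or 43 − 42 = 1, at any d; taper length = 14 − d.

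| | d = 0 | d = 3 | d = 7 |
|---|---|---|---|
| Days at 40 mg (14 + d) | 14 | 17 | 21 |
| A: drug-free days at last call | 7 | 4 | 0 |
| B: drug-free days at last call | 1 | −2 | −6 |
| C: drug-free days, call on day 49 / day 43 | 7 / 1 | 7 / 1 | 7 / 1 |
| C: taper length, days | 14 | 11 | 7 |

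Negative values mean that the participant is still dosing when called.

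**How many participants?** The documents give no delay rate, so this is an assumed range. With 0% delayed, nobody is affected. With 10% to 30% of 40 delayed, 40 × 0.10 = 4 to 40 × 0.30 = 12 participants lose some drug-free time under A. If delays spread evenly over 1 to 7 days (also assumed), 4/7 = 0.57 to 12/7 = 1.71 participants reach zero drug-free days. Delayed participants then average (6 + 5 + 4 + 3 + 2 + 1 + 0)/7 = 3 days instead of 7.

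**With the proposed rule.** The call falls on day 42 + d + 7 = 49 + d (day 49 to 56) under A and B, and on day 49 under C. Every reading then has at least 7 drug-free days.

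**The case against.** The strongest reply has four parts.

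1. **The 7 − d result is only one reading.** It needs a day-49 call and a full taper after the extension. Capping therapy at six weeks has support in 6.1.9, the Protocol Summary and the 42 days of capsules in 7.3.2, and then no drug-free time is lost. This stands as a limit, but does not remove the problem: the cap cuts the taper to as little as 7 days, and the text does not choose between the readings. Section 4.1 starts dosing at discharge for the group recruited in the monitoring unit; with a call counted from randomization, any such gap shortens drug-free time further.
2. **The named risk is sudden stopping, and these participants taper.** A day-49 call still covers the steps from 40 to 20 mg and from 20 to 10 mg. A delayed visit also brings the in-person check closer to that call: 49 − 35 = 14 days before it instead of 49 − 28 = 21. Nor does the protocol require any minimum drug-free period. All of this stands, and it is why the point is minor.
3. **Section 8.3 keeps recording open.** If a day-49 call counts as participation, recording runs to day 56, and known events are followed to resolution. That helps only with events that reach staff unprompted, because active questioning happens at scheduled contacts and none follows week 7.
4. **The larger ambiguity is the taper and the pill supply.** That is fair, and those points deserve an answer of their own. The call rule works whichever way they are settled.

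**Conclusion.** The concern holds as a minor, optional improvement. The protocol permits up to seven extra days at 40 mg and does not move the last AE call to match. With a day-49 call and a full taper, drug-free days at that call fall from 7 to 7 − d, and reach zero only when the whole extra week is used. With a day-43 call there is one drug-free day on time, and with the full extension the call comes 6 days before the last dose. With a six-week cap, drug-free time does not change with d.

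The result rests on dosing from randomization and on the stated readings of week 7 and of the taper, so confidence is medium. The number affected is unknown and probably small. Only active inquiry after the last dose is reduced. No bias between arms and no effect on the primary endpoints follows.

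**What to change.** In Section 7.3.4, write: *Final follow-up phone call at week 7, or 7 days after the participant's actual last dose, whichever is later.*

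The later-of rule keeps the week-7 call for anyone who stops early. The recording window in Section 8.3 should not be shortened. At most, add that for dosed participants it runs at least to this final call, and leave the rule for participants who are not randomized as it is.

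The cost is one sentence and an optional clause. It remains a single phone call. For extended participants, the call and close-out come up to one week later, at about week 8 with the full extra week. If calls are now made on day 43, on-time calls move by 49 − 43 = 6 days. Stating in 6.1.8 whether the full taper follows an extension, and reconciling the supply in 7.3.2 with 6.1.7, would be sensible in the same amendment, but the call rule does not depend on either.

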6.1.10 TRACKING OF DOSE

Phone follow up and counting pill in the pill container at follow up visit.

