7.3.7 SCHEDULE OF EVENTS TABLE

Procedures	Screening	Enrollment	phone call	ronow up phone call	Follow up visit	r filal Yellow up phone call				
Informed consent	X									
Demographics	X									
Medical history	X									
Iowa SSRI	X									
Sscreening Questionnaire	Λ									

Version 01.2 Protocol:201607761 Version 20.2 Version 01.2

Procedures	Screening	Enrollment	phone call	phone call	Follow up visit at week 4	up phone call				
Pregnancy screening questionnaire & urinary pregnancy test	X				X					
Medication history	X		X	X	X	X				
Iowa SSRI study questionnaire		X								
HCVR testing	X									
PHQ-9 score		X			X					
Randomization		X								
Video EEG & respiratory monitoring in EMU	Xª	Xª			Xb					
Adverse events evaluation			X	X	X	X				
Assessment of compliance			X	X	X					

a: Subjects enrolled from EMU

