8.1.1 DEFINITION OF ADVERSE EVENTS (AE)

Adverse event means any untoward medical occurrence associated with the use of an intervention, whether or not considered intervention-related.

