8.3 TIME PERIOD AND FREQUENCY FOR EVENT ASSESSMENT AND FOLLOW-UP

The occurrence of an AE or SAE may come to the attention of study personnel during study visits and interviews of a study participant presenting for medical care, or upon review by a study monitor. All AEs including local and systemic reactions not meeting the criteria for SAEs will be captured on the appropriate RF. Information to be collected includes event description, time of onset, clinician's assessment of severity, relationship to study product (assessed only by those with the training and authority to make a diagnosis), and time of resolution/stabilization of the event. All AEs occurring while on study must be documented appropriately regardless of relationship. All AEs will be followed to adequate resolution.

Any medical condition that is present at the time that the participant is screened will be considered as baseline and not reported as an AE. However, if the study participant's condition deteriorates at any time during the study, it will be recorded as an AE. UPs will be recorded in the data collection system throughout the study.

Changes in the severity of an AE will be documented to allow an assessment of the duration of the event at each level of severity to be performed. AEs characterized as intermittent require documentation of onset and duration of each episode.

The PI will record all reportable events with start dates occurring any time after informed consent is obtained until 7 days after the last day of study participation. At each study visit/followup phone visit, the investigator will inquire about the occurrence of AE/SAEs since the last visit. Events will be followed for outcome information until resolution or stabilization.

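### The final safety call is fixed at week 7 and does not follow the last dose, so a participant who uses the permitted extra week at 40 mg has at most one day off drug when it is made

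*Combined protocol and SAP*

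**What the plan says.** Section 6.1.7 sets 10 mg for one week, 20 mg for one week and 40 mg for two weeks, followed by "20 mg once a day for one week and 10 mg once a day for one week. Then STOP". Section 6.1.9 gives the duration of therapy as six weeks. Section 6.1.8 allows the 40 mg dose to continue "for maximum of an extra 1 week in case of delay in follow up appointment", which fits the one-week tolerance on the week-4 visit in section 7.3.3.

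After randomisation the scheduled contacts are calls at the end of weeks 1 and 3, the week-4 visit, and the final contact in section 7.3.4, a "Follow up phone call at week 7". That call collects adverse events and current medication. Section 7.3.5 provides no early termination visit.

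Section 8.3 records events "until 7 days after the last day of study participation".

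On adherence, section 6.1.10 specifies "Phone follow up and counting pill in the pill container at follow up visit", without dating the telephone checks. In the schedule table (7.3.7) the row "Assessment of compliance" is marked for the first two calls and the week-4 visit, but not for the final call.

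**The concern.** The purpose of a call after the end of dosing is to learn what happened once the drug was withdrawn. On the standard schedule the week-7 call can do this. The extra week moves the last dose but leaves the call where it is, so the two can coincide or fall in the wrong order.

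Two things are at stake. The first is safety capture for the individual: section 7.4 presents the titration schedule as the protection against withdrawal symptoms, and whether it worked can only be seen after the stop. The second is even ascertainment. Section 10.4.4 compares adverse event frequencies between arms, yet the time off drug that a scheduled question covers would differ between participants according to whether their visit was delayed.

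A smaller gap adds to this. The pill count takes place at the week-4 visit, normally before the step-down starts, and the final call does not ask directly about step-down doses. An event reported around the stop would then be hard to interpret.

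**Working it through.** **Inputs.** Dose durations from 6.1.7; extension of d = 0 to 7 days at 40 mg from 6.1.8; call timing from 7.3.4; recording window from 8.3. Day 1 is taken as both randomisation and first dose.

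**Check of the plan's own figure.** 7 + 7 + 14 + 7 + 7 = 42 days = 6 weeks, which agrees with 6.1.9.

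**Last dose with an extension.** Last dose day = 42 + d. For d = 7, 40 mg runs to day 35, 20 mg covers days 36-42, 10 mg covers days 43-49, and the last dose is day 49.

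**When the call falls.** Section 7.3.4 does not define week 7 to the day. Three readings bracket it: the first day of the seventh week (day 43), the last day of that week (day 49), or seven elapsed weeks (day 50). The last is reasonable because 7.3.3 counts the week-4 visit as time elapsed since randomisation.

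**Days off drug at the call** = call day − (42 + d). A negative value means the participant is still dosing.

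| Extra days d | Last dose | Call day 43 | Call day 49 | Call day 50 | Call at last dose + 7 |
|---|---|---|---|---|---|
| 0 | 42 | 1 | 7 | 8 | 7 (day 49) |
| 1 | 43 | 0 | 6 | 7 | 7 (day 50) |
| 3 | 45 | −2 | 4 | 5 | 7 (day 52) |
| 6 | 48 | −5 | 1 | 2 | 7 (day 55) |
| 7 | 49 | −6 | 0 | 1 | 7 (day 56) |

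**Set against 8.3.** The last day of participation is not defined. If it is the last dosing day, consistent with the six-week participant duration in the Protocol Summary, the window closes on day 42 + 7 = 49 as standard and on day 49 + 7 = 56 with the full extra week. A call on day 49 reaches the end of the first window. For the second, a call on days 43-49 covers none of the seven days and a call on day 50 covers one. If participation instead ends at the final call, the window runs seven days beyond it, again with no contact in that time.

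**How many participants.** The documents give no figure. Purely as an assumed range, if 10%, 25% or 50% of 40 completers used the full week, that would be 4, 10 or 20 people.

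**The case against.** The strongest reply is that the trigger is narrow and the gap partly filled. Participants on the standard schedule are called after the stop on every reading. With a call at the end of week 7, one to six extra days still leave six down to one days off drug. Section 8.3 also follows known events to resolution and accepts events noticed when a participant seeks care, and participants are patients of the same centre. All this stands. It limits the size of the problem, but it is passive capture and supplies no scheduled question after a day-49 stop.

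Adherence is partly covered too: 6.1.10 and 10.4.5 provide for telephone checks, and current medication is recorded at the final call. Step-down compliance cannot affect HCVR or PHQ-9 values already taken at the week-4 visit. The added question is therefore a minor improvement.

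A reader might go further in several ways that the documents do not support:

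- **That the call can never follow the stop after a full extra week.** On the elapsed-weeks reading it comes on day 50, one day after.
- **That the extension exposes participants to the sudden-stopping risk in 2.3.1.** The extra week is added before the step-down, which stays at two weeks.
- **That low mood and suicidal thoughts go unasked.** Adverse events are defined as such "whether or not considered intervention-related", and 8.3 adds that "All AEs occurring while on study must be documented appropriately regardless of relationship". Asking directly about mood might be more sensitive, but no stated rule fails without it. Screening at weeks 1 and 3 would also have a cost: under 5.4.1 a participant who newly meets an exclusion criterion may be terminated, and retention is a primary endpoint.
- **That arms would be compared unfairly.** Nothing in the documents suggests that delayed visits will differ by arm.

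The capsule supply listed in 7.3.2 does not match the step-down in 6.1.7. That is a separate matter, which retiming a call would not resolve.

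**Conclusion.** The point holds as a scheduling gap of limited reach. For a participant who uses the full extra week, the last scheduled contact falls from 6 days before the last dose to 1 day after it, against 1 to 8 days after it without an extension. The seven days following a day-49 stop therefore have at most one day of scheduled cover. Shorter extensions reduce the cover day for day.

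This rests on three assumptions. First, the full two-week step-down follows the extra week; 6.1.9 still says six weeks, but no rule shortens the step-down to fit. Second, dosing starts on the day of randomisation. Section 4.1 ties the start of dosing to discharge, and if it begins later while the call is counted from randomisation, the time off drug is shorter by the same number of days; a one-day lag would remove the single day left on the day-50 reading. Third, no contact is arranged outside the schedule.

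The number of participants affected is unknown. The exclusions for severe depression and for any history of suicidal ideation, together with the independent medical examiner's oversight, limit the risk. It is worth correcting because the correction is cheap.

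**What to change.** In 7.3.4 and 7.3.7, define the final call as 7 days after the last dose of study drug: day 49 on the standard schedule, 49 + d with an extension, day 56 at the latest. This uses the same seven days as 8.3. Add a question on step-down compliance to 7.3.4, and mark the compliance row of 7.3.7 for the final call.

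Cost: no new call or visit. Measured from day 49, the call moves by up to 7 days, and only for those who use extra days at 40 mg. For 40 completers the compliance question is asked 40 times. No endpoint or analysis changes.

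One trade-off should be accepted knowingly. For a day-35 visit with the full extra week, the interval from visit to final call rises from 49 − 35 = 14 days to 56 − 35 = 21 days, which equals the standard interval of 49 − 28 = 21. A call that might have fallen during the step-down then covers it only in retrospect.

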7.3.5 EARLY TERMINATION VISIT

NA

7.3.7 SCHEDULE OF EVENTS TABLE

Procedures	Screening	Enrollment	phone call	ronow up phone call	Follow up visit	r filal Yellow up phone call				
Informed consent	X									
Demographics	X									
Medical history	X									
Iowa SSRI	X									
Sscreening Questionnaire	Λ									

Version 01.2 Protocol:201607761 Version 20.2 Version 01.2

Procedures	Screening	Enrollment	phone call	phone call	Follow up visit at week 4	up phone call				
Pregnancy screening questionnaire & urinary pregnancy test	X				X					
Medication history	X		X	X	X	X				
Iowa SSRI study questionnaire		X								
HCVR testing	X									
PHQ-9 score		X			X					
Randomization		X								
Video EEG & respiratory monitoring in EMU	Xª	Xª			Xb					
Adverse events evaluation			X	X	X	X				
Assessment of compliance			X	X	X					

a: Subjects enrolled from EMU

